7.3.3.5 Other Safety Parameters

Other safety parameters include YMRS, EPS scales (AIMS, BARS, and SAS scores) and C-SSRS.

The number and percentage of patients with treatment-emergent mania will be presented by treatment group. Treatment-emergent mania will be defined as an YMRS total score of 16 or greater at any postbaseline visit. Descriptive statistics for YMRS total score and change from baseline values at each assessment time point will be presented by treatment group.

A patient will be considered to have treatment-emergent parkinsonism if the patient's SAS score was ≤ 3 at baseline and > 3 at any DB assessment. A patient will be considered to have treatment-emergent akathisia if the patient's BARS score was ≤ 2 at baseline and > 2 at any DB assessment. The number and percentage of patients reporting treatment-emergent parkinsonism or treatment-emergent akathisia will be tabulated by treatment group. Listings

of patients with treatment-emergent parkinsonism and patients with treatment-emergent akathisia will be provided and will include the patient identification number, study center number, and baseline and postbaseline values. Listings of all AEs occurring in patients who have treatment-emergent parkinsonism or treatment-emergent akathisia will also be provided.

Descriptive statistics for EPS scale parameters (AIMS, BARS, and SAS) and changes from baseline values at each assessment timepoint in this study will be presented.

The number and percentage of patients with suicidal ideation or suicidal behavior as recorded on the C-SSRS will be summarized by treatment group. The distribution of responses for most severe suicidal ideation and most severe suicidal behavior during the patient's lifetime, during the DB treatment period, and during the safety follow-up period will also be presented by treatment group for the safety population. Supportive listings will be provided and will include the patient identification number, study center number, lifetime history, and postbaseline values. Intensity of suicidal ideation, suicidal behavior type, and lethality of suicidal behavior will also be included in these listings. A listing of all AEs occurring in patients who have suicidal ideation or suicidal behavior will also be provided.

7.4 Other Analyses

Patient disposition, demographics and other baseline characteristics, prior and concomitant medication, extent of exposure and treatment compliance will be summarized and described in detail in the SAP.

Any potential additional analyses of efficacy and safety data due to the impact of COVID-19, (infection or disruption) on patient treatment (discontinuation or interruptions) and follow-up (data collection via alternative modality, missing or late visits, or complete lost-to-follow-up) will be described in the SAP.

7.4.1 Pharmacokinetic Parameters

Plasma samples will be analyzed for the concentrations of cariprazine and its metabolites DCAR and DDCAR using a validated bioanalytical method. A population PK approach will be used to estimate individual-level drug-exposure parameters (eg, steady-state area-under-the-curve [AUC], steady-state maximum concentration [C_{\max}], steady-state minimum concentration [C_{\min}]) for each of the 3 analytes. This will be performed via the use of appropriate nonlinear mixed-effects modeling software. The relationship, if any, between effectiveness and drug-exposure parameters will be explored. These analyses will be reported separately.

7.4.2 Health Outcome Measure Analyses

The SF-12 will be administered at Visit 2 and Visit 6/ET.

Analysis of change from baseline in the PCS-12 and MCS-12 score at Week 6 will be conducted using the ANCOVA model that has treatment group and study center as factors and the baseline value as the covariate.

7.5 Subgroup Analyses

To determine whether the treatment effect is consistent across various subgroups, the estimate of the between-group treatment effect (with a 95% CI) for each cariprazine dose versus placebo for the primary efficacy variable will be estimated within each category of the following classification variables:

- ADT failure category (one ADT failure, more than one ADT failure)
- Region (US, NonUS)

7.6 Interim Analyses

No interim analysis is planned for this study.

7.7 Sample Size Calculation

The study will randomize approximately 750 patients in a 1:1:1 ratio to cariprazine 1.5 mg/day, cariprazine 3 mg/day, and placebo groups. A sample size of 250 patients per arm will provide approximately 84% statistical power to show statistically significantly higher effect in each dose of cariprazine versus placebo based on the mITT analysis set. The study has approximately 90% statistical power to show that at least 1 of the 2 cariprazine doses is statistically significantly more efficacious than placebo in the primary endpoint. These calculations assumed an effect size of 0.286. All statistical powers presented in this section were calculated adjusting for multiple comparisons using the Hochberg procedure with the family-wise type I error rate being controlled at a 0.05 level (2-sided). The dropout rate is assumed to be 15% at Week 6. Within-person correlation for the primary endpoint is assumed to be 0.58. This value is used in the sample size calculation to calculate an inflation factor that accounts for information loss due to the missing data at Week 6 for longitudinal data collection.

Assumptions of effect size, intracorrelation and dropout rate are based on cariprazine Study RGH-MD-75.

8 Study Visit Schedule and Procedures

Please see [Table 1](#) for a schematic of the schedule of visits and procedures, and Section [6](#) for details of tests and rating scales.

8.1 Patient Entry Procedures

8.1.1 Overview of Entry Procedures

Prospective patients as defined by the criteria in Sections [4.3](#) and [4.4](#) (inclusion/exclusion criteria) will be considered for entry into this study.

8.1.2 Informed Consent and Patient Privacy

The study will be discussed with the patient and a patient wishing to participate must give informed consent prior to any study-related procedures or change in treatment. The patient must also give authorization (United States only), data protection consent (Europe only), and other written documentation in accordance with the relevant country and local privacy requirements (where applicable) prior to any study-related procedures or change in treatment.

Each patient that provides informed consent will be assigned a patient number that will be used on patient documentation throughout the study.

Where applicable, a central vendor will be used to verify patients' current and past research study status in order to mitigate safety concerns associated with duplicate enrollment and protocol deviations associated with multiple trial enrollment. Following proper informed consent and after issuing a patient number, each patient will be reviewed in the Verified Clinical Trials (VCT) database, indicated in the schedule of visits and procedures ([Table 1](#)). Partial identifiers will be utilized. Patients who are identified as verification failures by VCT should not continue participation without documented approval from the Sponsor.

8.2 Washout Interval

Patients with MDD with inadequate response to ongoing ADT in the current episode will undergo a washout of prohibited medications for up to 14 days during the screening period, with up to an additional 7 days if needed with Sponsor approval (see Section [4.5.2](#)). During the washout, the patients will continue to take the ADT that they are not responding to.

The length and timing of the washout of prior psychiatric medications during the 14 days allotted for the screening period is at the discretion of the investigator (with up to an additional 7 days if needed with Sponsor approval). Prior medications should be gradually withdrawn such that the washout is completed by Baseline (Visit 2). Please note that during the washout period psychotropic medications other than those listed as rescue (Section 4.5.3) may not be newly initiated or reinitiated.

8.3 Procedures for Final Study Entry

Final study eligibility, for patients meeting SAFER criteria, will be determined at Visit 2 (Baseline Visit). Patients should continue to meet the inclusion and exclusion criteria as specified in Sections 4.3 and 4.4.

A patient is considered to have entered the study at the time of randomization to treatment at Visit 2 (Baseline).

Rescreening of screen failures is permitted in certain situations after consultation with the Allergan Medical Monitor.

See Section 5.4 for the method for assignment to treatment groups/randomization.

8.4 Visits and Associated Procedures

The schedule of study procedures and assessments is tabulated by visit in the schedule of visits and procedures in (Table 1). A description of individual procedures is provided in Sections 6.1, 6.2, 6.3, 6.4, 6.5, and 6.6. Evaluations should be performed by the same evaluator throughout the study whenever possible. During the study, every effort should be made to perform the study procedures as indicated in (Table 1). The descriptions of the procedures to be performed at each visit are provided below.

As a result of the ongoing COVID-19 pandemic, some in-person study visits may not be possible due to public health concerns. When these public health concerns interfere with the conduct of in-person clinic visits, site visits may be conducted via an alternative format. Refer to Section 12.2 for allowable protocol modifications during the COVID-19 pandemic.

8.4.1 Screening (Visit 1)

The following procedures will be carried out at Screening (Visit 1):

- Obtain informed consent and patient privacy authorization/consent; consent for pharmacogenetic sampling may also be obtained
- Access IWRS to register the patient and assign a patient identification number
- Perform Verified Clinical Trials check
- Assess inclusion/exclusion criteria
- Collect and assess medical and psychiatric history
- Administer and assess SCID-5
- Collect blood samples for hepatitis serology
- Collect samples for UDS
- Perform blood alcohol concentration assessment with Breathalyzer
- Collect blood samples for serum pregnancy test (women of childbearing potential only)
- Collect blood samples for clinical laboratory tests
- Collect blood sample for hemoglobin A1c
- Review prior and concomitant medications
- Assess modified ATRQ, MADRS, HAMD-17, CGI-S, C-SSRS and YMRS
- Collect vital signs measurements, including weight and height
- Perform physical examination
- Perform ECG and transmit to central reader
- Review and assess AEs and SAEs
- For patients meeting initial inclusion/exclusion criteria, schedule and ensure the SAFER interview is conducted prior to Visit 2 (Baseline Visit)

8.4.2 Baseline (Visit 2)

The following procedures will be carried out at Baseline (Visit 2):

- Evaluate results from SAFER interview to confirm patient eligibility to continue in study
- Assess all other inclusion/exclusion criteria
- Review concomitant medications and assess ADT compliance
- Assess MADRS, HAMD-17, HAM-A, YMRS, CGI-S and C-SSRS
- Evaluate EPS (AIMS/BARS/SAS)
- Administer SF-12
- Collect vital signs measurements (including weight and waist circumference)
- If not already obtained at Screening (Visit 1), obtain consent for and collect blood for the pharmacogenetic sample. Consent for pharmacogenetic sampling may be obtained any time between Visit 1 and Visit 6/ET, inclusive. A single sample can be obtained any time between Visit 2 and Visit 6/ET, inclusive
- Review and assess AEs and SAEs
- Access IWRS to randomize patient and then dispense IP

8.4.3 Double-blind Treatment Period (Visits 3 to 6/ET)

The following procedures will be carried out during the DB treatment period at every visit except as noted:

- Review concomitant medications and assess ADT compliance
- Collect IP blister cards, perform drug accountability and assess IP compliance
- Assess MADRS, CGI-S, CGI-I, and C-SSRS; HAM-A (Visits 4 and 6/ET only), YMRS (Visit 6/ET only) and HAMD-17 (Visit 6/ET only)
- Evaluate EPS (AIMS/BARS/SAS)
- Administer SF-12 (Visit 6/ET only)
- Collect vital signs measurements (including weight)
- Collect waist circumference measurement (Visit 6/ET only)

- Review and assess AEs and SAEs
- Collect blood sample for serum pregnancy test for women of childbearing potential (Visit 6/ET only)
- Collect blood samples for clinical laboratory determinations (Visit 6/ET only)
- Collect blood for PK evaluation (any time during Visits 4, 5 and 6/ET)
- If not already obtained previously, obtain consent for and collect blood for the pharmacogenetic sample. A single sample can be obtained at any time between Visit 2 and Visit 6/ET, inclusive
- Perform ECG (Visit 6/ET only)
- Perform physical examination (Visit 6/ET only)
- Access IWRS to dispense IP (Visit 3 through Visit 5), and register patient completing Visit 6/ET

Note: After completion of Visit 6/ET, patients will receive treatment for their MDD as deemed necessary by the Investigator or designee.

8.4.4 Safety Follow-up (Visit 7)

The following procedures will be carried out at the Safety Follow-up Visit (Visit 7/Week 10):

- Review concomitant medications
- Collect vital signs measurements (including weight)
- Collect blood sample for serum pregnancy test (women of childbearing potential only)
- Review and assess AEs and SAEs
- Assess C-SSRS

8.5 Instructions for the Patients

- Patients are to be instructed to take their study medication daily around the same clock time, with or without food; study medication should not be taken with grapefruit juice

- Patients are to continue to take their ADT as instructed throughout the study and to bring their ADT to visits for compliance review
- Patients are to be reminded to return used/partially used IP blister cards at every study visit
- The Investigator (or designee) is to ensure that concomitant medications are reviewed against the prohibited and allowed rescue medications detailed in Sections [4.5.2](#) and [4.5.3](#); patients are to be advised accordingly. If the permissibility of a specific medication/treatment is in question, the Investigator should consult the Allergan Medical Monitor.
- Patients are to be asked to limit alcohol consumption and abstain from using illicit drugs during the study
- Patients are to be asked to fast for at least 10 hours before blood and urine samples are collected at Screening (Visit 1) and Visit 6/ET

8.6 Unscheduled Visits

Unscheduled visits can be performed if safety concerns arise and at the discretion of the Investigator. Additional examinations may be performed as necessary to ensure the safety and well-being of patients during the study. An eCRF will be completed for each unscheduled visit.

8.7 Compliance with Protocol

Participating patients should be able to adhere to the completion of required questionnaires and testing parameters as described in this protocol.

Data will be recorded on the appropriate eCRF supported by appropriate source documentation. At each visit, patients should be asked if any concomitant medications had been used, if they had undergone any concurrent procedures (nonstudy procedures), and if they had been in compliance with the protocol since the previous visit.

For compliance with IP and ADT see Sections [5.6.1](#) and [5.6.2](#), respectively.

8.8 Early Discontinuation of Patients

Patients may discontinue from the study at any time for any reason. Discontinuation is permanent; once a patient is discontinued, he/she shall not be allowed to enroll again.

Patients can be prematurely discontinued from the study and subsequently enter the safety follow-up period for one of the following reasons:

- AE
- Noncompliance with protocol
- Noncompliance with IP dosing regimen and/or ongoing ADT dosing regimen
- Withdrawal of consent (a clear reason must be documented when possible)
- Patient decision to not continue in the study
- Lost to follow-up (every effort must be made to contact the patient; a certified/traceable letter must be sent)
- Study terminated by Sponsor
- Site terminated by Sponsor
- Pregnancy
- Other reasons

Notification of early patient discontinuation from the study and the reason for discontinuation will be clearly documented on the appropriate eCRF page. Patients who take IP during the study and who prematurely discontinue from the study, regardless of cause, should be seen for a final assessment. A final assessment will be defined as completion of the evaluations scheduled for Visit 6/ET. If the patient discontinues after IP is taken, the patient is also expected to return for the Safety Follow-up Visit (Visit 7) 4 weeks after completion of the ET Visit.

At a minimum, the following information should be collected when a patient is discontinued:

1. The reason the patient discontinued
2. The date of the last dose of IP taken by the patient. All IP should also be retrieved from the patient.
3. The date of the last study assessment and/or contact. A follow-up contact (telephone or visit) will be arranged as appropriate

4. (S)AEs

5. Compliance with the IP administration as specified in this protocol

6. Final Assessments: Unless there is withdrawal of consent, every effort should be made to ensure that all procedures and evaluations scheduled for Visit 6/ET and subsequently Visit 7 (Safety Follow-up Visit) are performed ([Table 1](#), and Section [8.4](#)).

Discontinued patients will not be replaced, and re-screening will not be allowed.

8.9 Withdrawal Criteria

It is the right and the duty of the Investigator or subinvestigator to stop treatment in any case in which emerging effects are of unacceptable risk to the individual patient. In addition, the Investigator or subinvestigator is to stop treatment of any patient with unmanageable factors that may interfere significantly with the trial procedures and/or the interpretation of results.

A patient must be discontinued from the study for any of the following reasons:

1. The patient misses ≥ 4 consecutive doses of IP and/or ongoing ADT
2. The patient required or initiated hospitalization for his/her psychiatric symptoms
3. The patient decompensates psychiatrically (becomes acutely suicidal, homicidal or psychotic) and in the judgment of the Investigator cannot be safely managed in the study
4. The patient has a positive UDS at any time during the study; for exceptions see Exclusion Criterion 4 and Section [4.5.3](#)
5. The patient experiences 1 of the following elevated liver enzyme conditions, which is confirmed by repeat testing:
 - ALT or AST $> 3 \times$ ULN and total bilirubin $> 2 \times$ ULN
 - ALT or AST $> 8 \times$ ULN
 - ALT or AST $> 5 \times$ ULN for more than 2 weeks

- ALT or AST $> 3 \times$ ULN with the appearance of jaundice, worsening of fatigue, nausea, vomiting, right upper quadrant pain or tenderness, fever, rash, or eosinophilia

6. The patient has an absolute neutrophil count (ANC) of < 1000 per mm³ and, after repeat testing within 24 hours of awareness, the values are not normalized or are not increasing
7. A female patient becomes pregnant during treatment

8.10 Study Termination

The study may be stopped at a study site at any time by the site investigator. The Sponsor may stop the study (and/or the study site) for any reason with appropriate notification.

9 Adverse Events

AEs occurring during the study will be recorded on an AE eCRF. If AEs occur, the first concern will be the safety of the study patients.

9.1 Definitions

9.1.1 Adverse Event

An AE is any untoward medical occurrence in a patient or clinical investigation patient administered a pharmaceutical product and that does not necessarily have a causal relationship with this treatment. An AE can therefore be any unfavorable and unintended sign (including an abnormal laboratory finding), symptom, or disease temporally associated with the use of a medicinal (investigational) product, whether or not related to the medicinal (investigational) product. In addition, during the screening period, AEs will be assessed regardless of the administration of a pharmaceutical product.

Note: AEs must be collected once informed consent has been obtained, regardless of whether or not the patient has been administered IP.

Progression of treatment indication, including new or worsening of anticipated clinical signs or symptoms, which are collected as clinical efficacy variables and assessed as unequivocally associated with the disease progression and/or lack of efficacy, should NOT be reported as AEs unless the disease progression is greater than anticipated in the natural course of the disease.

AEs will be assessed, documented, and recorded in the eCRF throughout the study (ie, after informed consent has been obtained). At each visit, the investigator will begin by querying for AEs by asking each patient a general, non-directed question such as “How have you been feeling since the last visit?” Directed questioning and examination will then be done as appropriate. All reported AEs will be documented on the appropriate eCRF.

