6.2.1.1 Montgomery-Åsberg Depression Rating Scale

The MADRS ([Montgomery and Åsberg, 1979](#)) is a 10-item, clinician-rated scale that evaluates the patient's depressive symptomatology during the past week. Patients are rated on items assessing feelings of sadness, lassitude, pessimism, inner tension, suicidality, reduced sleep or appetite, difficulty in concentration, and lack of interest. Each item is scored on a 7-point scale with a score of 0 reflecting no symptoms and a score of 6 reflecting symptoms of maximum severity.

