6.2.2.4 Hamilton Depression Rating Scale–17 Items

The HAMD-17 ([Hamilton 1960; Hamilton 1967; Miller et al, 1985](#)) is a clinician-rated, 17-item scale used to rate the patient's depressive state based on feelings of depression, guilt, suicidality, anxiety, agitation, level of insight, patterns of insomnia, loss of interest in work and other activities, weight loss, hypochondriasis, and degree of psychomotor retardation. It also can be used to identify genital and somatic symptoms. This instrument will be administered by an experienced rater meeting the training requirements and qualifications set by the Sponsor.

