9.1.2 Serious Adverse Event

An SAE is any AE occurring at any dose that results in any of the following outcomes: death, is life-threatening, inpatient hospitalization or prolongation of existing hospitalization, a persistent or significant disability/incapacity, or a congenital anomaly/birth defect. Important medical events that may not result in death, be life-threatening, or require hospitalization may be considered an SAE when, based upon appropriate medical judgment, they may jeopardize the patient and may require medical or surgical intervention to prevent one of the outcomes listed in this definition (see Section 9.3 for procedures for reporting SAEs).

Allergan considers all cancer AEs as SAEs. In addition, Allergan considers any abortion (spontaneous or nonspontaneous) as an SAE.

Preplanned surgeries or procedures for pre-existing, known medical conditions for which a patient requires hospitalization is not reportable as an SAE.

Any preplanned surgery or procedure should be clearly documented in the site source documents by the Investigator or designee at the time of the patient’s entry into the study. If it has not been documented at the time of the patient’s screening visit (Visit 1), then it should be documented as an SAE and reported to Allergan.

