The safety analysis will be performed using the safety population for the double-blind treatment period and safety follow-up period. The double-blind treatment period starts with the first dose of double-blind investigational product and ends with the last scheduled assessment at Visit 6 (Week 6) or early termination (before Week 6). The safety follow-up period starts the day after the last scheduled assessment at Visit 6 (or early termination) and ends with the last safety follow-up visit. The safety parameters will include adverse events (AEs), clinical laboratory parameters, vital signs, electrocardiogram (ECG) parameters, EPS scales, the C-SSRS and the YMRS. For each safety parameter, the last assessment made before the first dose of double-blind investigational product will be used as the baseline for all analyses of that safety parameter. The summarization will be by treatment group for both double-blind and safety follow-up periods. Continuous variables will be summarized by number of participants and mean, SD, median, minimum, and maximum values. Categorical variables will be summarized by number and percentage of participants.

10.1 **ADVERSE EVENTS**

Adverse events will be coded by system organ class and preferred term using the *Medical Dictionary for Regulatory Activities*, version 24.0.

An adverse event (AE) will be considered a treatment-emergent adverse event (TEAE) if the AE began or worsened (increased in severity or became serious) on or after the first dose of DB investigational product. Per case report form instructions, a new AE record will be created with a new AE onset date for any AE that worsens. Therefore, TEAEs can simply be identified as those AEs with recorded onset date (and time, if known) on or after the date of the first dose of study intervention.

An AE will be considered a TESAE if it is a TEAE that additionally meets any SAE criterion.

For the DB treatment period, the number and percentage of participants reporting TEAEs in each treatment group will be tabulated by system organ class and preferred term; by system organ class, preferred term, and severity; and by system organ class, preferred term, and relationship to the IP. If more than 1 AE is coded to the same preferred term for the same participant, the participant will be counted only once for that preferred term using the most severe and most related occurrence for the summarization by severity and by relationship to the IP.

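### A psychiatric hospitalisation judged to be MDD progression can be left out of the AE and SAE data, because the disease-progression exception in Protocol 9.1.1 has no override for serious events.

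*Protocol*

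**What the plan says.** Four provisions have to be read together.

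- **Protocol 9.1.1 (Adverse Event).** The exception covers "Progression of treatment indication, including new or worsening of anticipated clinical signs or symptoms, which are collected as clinical efficacy variables" and that are "assessed as unequivocally associated with the disease progression and/or lack of efficacy". Such events "should NOT be reported as AEs unless the disease progression is greater than anticipated in the natural course of the disease".
- **Protocol 9.1.2 (Serious Adverse Event).** "An SAE is any AE occurring at any dose that results in any of the following outcomes"; inpatient hospitalisation is one of those outcomes. SAP 10.1 follows the same structure: "An AE will be considered a TESAE if it is a TEAE that additionally meets any SAE criterion".
- **Protocol 8.9 (Withdrawal Criteria), criterion 2.** A patient must be discontinued if "The patient required or initiated hospitalization for his/her psychiatric symptoms". Criterion 3 adds psychiatric decompensation that the investigator judges cannot be managed safely in the study.
- **Protocol 6.2.1.1 and 6.2.2.4.** The symptoms that count as efficacy variables are broad. For the MADRS, "Patients are rated on items assessing feelings of sadness, lassitude, pessimism, inner tension, suicidality", among others. The HAMD-17 rates the "depressive state based on feelings of depression, guilt, suicidality, anxiety, agitation" and further items.

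Suicidality also has its own safety measure. The C-SSRS is completed at all visits (Protocol 6.6.6.2) and summarised by treatment group (Protocol 7.3.3.5, SAP 10.5.3).

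**The concern.** Safety and tolerability are part of the study objective (Protocol 2.1), and the drug is meant to act on the same symptoms that the exception covers. The site decides attribution before the event enters the database. It does so blinded, with no criterion for when a link is unequivocal or when progression exceeds what was anticipated.

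An event stopped at the AE step has no AE record to which seriousness can attach. For a psychiatric admission, three things are at stake: its place in the TEAE and TESAE summaries and the SAE listing, its place in the table of AEs leading to discontinuation, and the report to the sponsor within 24 hours (Protocol 9.3). An admission is among the most serious outcomes that a depression trial can observe, so its reporting should not depend on an undefined judgement.

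**Working it through.** The plan states no figure on this point, so there is none to reproduce. The check is mainly textual.

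**Step 1: the chain of definitions.**

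| Level | Source | Condition for entry |
|---|---|---|
| AE | Protocol 9.1.1 | Untoward occurrence, unless the progression exception applies |
| SAE | Protocol 9.1.2 | Must be an AE, with a serious outcome |
| 24-hour report | Protocol 9.3 | Must be an SAE |
| TESAE | SAP 10.1 | Must be a TEAE that meets an SAE criterion |

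Each level after the first takes its members from the level above. An exclusion at AE level therefore passes down to all of them.

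**Step 2: is there a route back?** Nothing in Protocol 9.1.2, Protocol 9.3 or SAP 10.1 says that a disease-related event meeting a seriousness criterion is reported anyway. The protocol does use such overrides elsewhere. Potential Hy's law cases (9.5) and pregnancies (9.4) are reported even where there is no AE. Ocular events of special interest are notified whether or not they are serious (6.6.2).

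**Step 3: is a psychiatric admission captured in another table?** Criterion 2 of Protocol 8.9 forces withdrawal, but the discontinuation reasons in Protocol 8.8 name neither hospitalisation nor lack of efficacy. On that list an admission could be coded as an AE or under other reasons. SAP 6.0 summarises the recorded reasons by arm, so the withdrawal is counted but the admission need not be identifiable. As the C-SSRS is described in Protocol 6.6.6.2, it records ideation, behaviour and lethality, not admission.

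**Step 4: scale, by assumption only.** The documents give neither a rate of serious psychiatric worsening nor the share that would be classed as progression. Assume a rate r of 0.5% to 2%. Per arm, 250 × 0.005 = 1.25 and 250 × 0.02 = 5 events. Across the trial, with excluded share e, the expected count is 750 × r × (1 − e).

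SAP 10.1 provides summary tables for TESAEs if they occurred in 5 or more participants. Taking these events alone, the chance of reaching 5 is P(X ≥ 5) with X ~ Binomial(750, r(1 − e)):

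| r | e = 0: expected; P | e = 0.5: expected; P | e = 0.75: expected; P |
|---|---|---|---|
| 0.5% | 3.75; 0.32 | 1.88; 0.04 | 0.94; 0.003 |
| 1% | 7.5; 0.87 | 3.75; 0.32 | 1.88; 0.04 |
| 2% | 15; >0.99 | 7.5; 0.87 | 3.75; 0.32 |

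With counts this small, the attribution step could decide whether the events reach the threshold. Patients with SAEs are listed whatever their number, but an event that was never reported as an AE is not in that listing either.

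**Step 5: direction.** If worsening is commoner on placebo, the exclusion removes mainly placebo events and could make the drug look relatively worse. If the drug causes psychiatric worsening, it removes mainly events in the active arms. Nothing in the documents says which dominates.

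**The case against.** The strongest reply is that the exception is narrow. The symptom must be anticipated and collected as an efficacy variable, the link must be unequivocal, and progression must not exceed what was expected. If a blinded investigator cannot tell a drug effect from lack of efficacy, the link is not unequivocal and the event is an AE. The patients are outpatients, and those with a suicide attempt in the past year or at significant suicide risk are excluded (Protocol 4.3 criterion 4; 4.4 criterion 6). An admission can therefore readily be read as progression beyond what was anticipated. The only hospitalisations that 9.1.2 exempts are for preplanned surgery or procedures.

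This stands to the extent that loss is possible, not automatic. A reader might infer that an admission attributed to MDD is always neither an AE nor an SAE; the conditions in 9.1.1 do not support that. The reply does not close the gap, because the deciding judgements have no criteria and no sentence states the outcome for a serious event.

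A second reply is that psychiatric safety is measured in other ways. Ideation and behaviour are compared by arm through the C-SSRS. Akathisia and restlessness are covered by the BARS and the EPS TEAE summaries, and mania by the YMRS. Agitation treated with rescue medication is documented (Protocol 4.5.3) and tabulated by arm (SAP 7.0). This also stands. A reader might infer that suicidality drops out of the safety comparison, but the C-SSRS analyses contradict that. What remains exposed is its AE/SAE coding and expedited reporting, and the planned listing of AEs in patients with suicidal ideation or behaviour, which depends on AE reporting. None of these sources identifies a psychiatric admission.

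**Conclusion.** The concern holds in a limited form. As written, 9.1.1 lets a psychiatric hospitalisation judged to be MDD progression stay out of the AE/SAE tables and the 24-hour report. The same admission forces withdrawal under 8.9 and has no table of its own. How often this would happen depends on investigator judgement.

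The size is unknown. The rates of 0.5% to 2% and the excluded shares are illustrative assumptions, and all that follows from them is that the counts are small enough for a few reclassified events to matter. A reader might infer a bias towards no difference between arms; the documents do not support any direction. Safety is summarised descriptively, so no confirmatory test is affected. The point concerns complete ascertainment and prompt reporting of serious events.

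**What to change.** Add one sentence to Protocol 9.1.1, with a cross-reference in 9.1.2: *This exception does not apply to any event that meets a seriousness criterion in Section 9.1.2, including psychiatric hospitalisation and serious suicidal behaviour; such events are reported as AE/SAE whatever their attribution.* Carry the same instruction into the eCRF completion guide.

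Optionally, tabulate withdrawals under criteria 2 and 3 of Protocol 8.9 by arm in the SAP, so that psychiatric admissions and decompensations can be compared directly. The C-SSRS analyses stay as they are.

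Label: cheap improvement. It needs an amendment sentence and, if taken up, one SAP table. It adds no assessment and does not alter patient management. The downside is a few more AE/SAE reports, some of which will reflect the underlying illness.
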